5.2 Alternate/Further treatment and evaluation

Where any participant fails to respond adequately to study treatment and moderate-severe anemia persists despite iron therapy, such participants will be further evaluated for other forms of anemia and/or referred to specialist hematologist for further evaluation of other causes of anemia at any point during follow up. Relevant information on alternate or additional treatment must completed in the source document and the e-CRF and the participants must be followed up to the end of the study.

5.3 Loss to follow up

If a participant fails to appear for a scheduled visit, at least three attempts to contact her will be made over the subsequent 30 days. These attempts will be documented in the participant study file. Her file will remain open until by calculation, she would have completed 6+1-month post-partum.

For participants who are lost to follow-up (i.e., those patients whose status is unclear because they fail to appear for study visits without stating an intention to withdraw), the RN should show "due diligence" by documenting in the source documents (visitation and call logs; *Appendix xvii*) steps taken to contact the participant, e.g., dates and numbers of phone calls, home visit, etc.

If the participant does not return to the study before she had completed 6+1-month post-partum, the end of study form will only be completed at her completed 7 months post-partum. The form will indicate that the participant was lost to follow up. The "lost to follow up" designation cannot be made for any participant until the natural end of her study visits which is 6+1-month post-partum.

6 STUDY PRODUCTS, INVENTORY & TREATMENT

6.1 Study Drugs

- IV ferric carboxymaltose
- Oral ferrous sulphate

6.2 Study drug supply and resupply, storage, and tracking

- Study drugs will be received by a designated person at the study site, handled and stored safely and appropriately, and kept in a secured location to which only the investigator and designated assistants have access.
- Upon receipt, all study drugs should be stored according to the instructions specified on the drug labels.
- Study drugs and all clinical supplies are to be dispensed only in accordance with the protocol.
- The site coordinator and research nurses must maintain an accurate record of supplies and dispensing of study drugs in the *drug accountability ledgers* (Appendix xviii).
- Monitoring of drug accountability will be performed by the clinical monitor during site visits and at the completion of the trial.
- Participants may be asked to return all unused study drug and packaging at the end of the study or at the time of study drug discontinuation.

6.3 Dispensing the study drug and labeling

- Each study site will be supplied with the study drugs by the trial pharmacist.
- Once a patient at a particular site is randomized. The site coordinator or research nurse assistant will identify the study drug to dispense to the patient based on the randomization arm.
- Immediately before dispensing the study drug to the patient, site coordinator/RN will document into all required the source documents (enrollment log, patients case notes and drug accountability ledger) and e-CRF with the participant's unique Study ID.

6.4 Other concomitant treatment and medication

Use of any other drug unprescribed and herbal medications are strongly discouraged. However, if taken, the information should be collected in the e-forms under co-medications. Participants will be specifically requested not to take any other iron containing medication.

6.5 Study drug discontinuation

- Study drug must be discontinued for a given participant if the investigator determines that continuing it would result in a significant safety risk for that patient. This should only be done after discussion with and approval from the chief investigator/PI.
- The following circumstances require study drug discontinuation:
 - Emergence of severe adverse reactions such as severe nausea/vomiting, allergy, severe pruritus, anaphylaxis, and other life-threatening symptoms
 - Abnormal laboratory values: Hb <6g/dl

Participants who discontinue study drug for adverse effects (AE) or any reason other than an AE will be followed to study completion at 6 months postpartum at which times all the assessments as listed for the visits will be performed. Reasons for study drug discontinuation should be completed, giving the date and primary reason for stopping the study drug under the relevant section of the CRF.

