7.2 Reporting Adverse Events (AEs)

- All adverse events that occur from the point of enrollment and throughout study duration will be collected non-systematically from each participant. Participants will be routinely asked at every study visit "do you have any symptoms now or noticed any since your last visit?"
- If a participant reports an AE at enrollment but before the administration of study intervention, the AE will be reported as not related to study drug. All other adverse events reported after enrollment into the study and until the end of study will be defined and graded for severity using the National Cancer Institute Common Terminology Criteria for Adverse Events version 5.0
- Study site coordinators/clinician will document on the appropriate study e-CRF, and clinical case notes all AEs reported by or observed in enrolled study participants regardless of severity and presumed relationship to study product.
- The study clinician must provide on the AE e-form information on symptoms, time of onset, severity, frequency, product-relatedness, actions taken and participant outcome.
- The causality of AE to trial drugs will be determined by the principal investigator and documented along with the interventions given, and the outcome.
- The PI may request additional information from the site if it is needed to further evaluate the AE.

- Site coordinators will report serious adverse events (SAEs; see section 7.2.5) to the principal Investigator and the local Ethics committee as soon as possible and in accordance with the local ethics committee requirements.
- Discontinuation of study drug may be considered if a participant experiences a severe adverse drug event of Grade 3 or higher. Decision for discontinuation will be made by the PI and or the study participant. Study personnel will document the circumstances and data leading to discontinuation.

All adverse events must be recorded on the e-CRF with the following information:

- 1. Event (nomenclature/description) (See section 7.2.1)
- 2. The severity grade (mild, moderate, severe, life threatening or death) (see section 7.2.2)
- 3. Its relationship to the study drug(s) (see section 7.2.3)
- 4. Its duration (start and end dates or if continuing at final physical exam)
- 5. Whether it constitutes a serious adverse event (SAE)
- 6. Action taken (Treatment)
- 7. Outcome

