7.2.7 Treatment of adverse events

All adverse events should be treated appropriately. Treatment may include one or more of the following:

- No action taken (i.e., further observation only).
- Study drug dosage adjusted/temporarily interrupted.
- Study drug permanently discontinued due to this adverse event.
- Concomitant medication given.
- Non-drug therapy given.
- Patient hospitalized/patient's hospitalization prolonged.

The action taken to treat the adverse event should be recorded on the adverse event e-CRF.

- Once an adverse event is detected, it should be followed up until its resolution or until it is judged to be permanent, and assessment should be made at each visit (or more frequently, if necessary) of any changes in severity, the suspected relationship to the study drug, the interventions required to treat it, and the outcome.
- Information about common side effects already known about the investigational drug will be included in the patient informed consent and should be discussed with the patient during the study as needed.

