7.3.1 Safety issues with ferric carboxymaltose

7.3.1.1 Hypersensitivity reactions (HSRs)

Parenterally administered iron preparations including FCM can cause hypersensitivity reactions including serious and potentially fatal anaphylactic/anaphylactoid reactions (39). The risk is enhanced for patients with known allergies including druq allergies, patients with a history of severe asthma, eczema, or other atopic allergies. There is also an increased risk of hypersensitivity reactions in patients with immune or inflammatory conditions (e.g., systemic lupus erythematosus, rheumatoid arthritis). **These conditions with increased risk for HSRs are excluded from this study.**

Other risk factors for hypersensitivity reaction are previous reaction to intravenous iron, fast iron infusion rate and staff or patient anxiety.

- FCM should only be administered when study staff that are trained to evaluate and manage anaphylactic reactions are immediately available and, in an environment, where full resuscitation facilities can be assured.
- Each patient should be observed for adverse effects for at least 30 minutes following FCM administration. If hypersensitivity reactions or signs of intolerance occur during administration, the infusion must be stopped immediately, and the resuscitation protocol activated (*Refer to IVON Trial Protocol No: 02; Administration of Intravenous Ferric Carboxymaltose and the Emergency Treatment of Hypersensitivity Reaction Type 1 (Anaphylaxis).*
- Facilities for cardiorespiratory resuscitation and equipment for handling acute anaphylactic/anaphylactoid reactions should be available, including an injectable 1:1000 adrenaline solution. Additional treatment with antihistamines and/or corticosteroids should be given as appropriate.

CAUTION:

- Acute hypersensitivity reactions during iron infusions are very rare but can be life-threatening and so these special precautions must be always considered.
- Every administration of FCM:
 - Must be preceded by a recheck for risk factors for an HSR, the general condition of the patient and base-line observations including pulse rate, blood pressure and respiratory rate.
 - The infusion should be prepared as stated in the manufacturer's instructions.
 - Infusion should be initiated slowly and not increased until it is clear that it is being welltolerated (usually after 5-10 min).

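### For a severe drug reaction, section 6.5 requires study drug to be discontinued while section 7.2 makes it optional, and the two only partly agree on who decides

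*Protocol*

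**What the plan says.** Four places in the protocol bear on stopping study drug after a reaction.

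- **Section 6.5, first bullet.** "Study drug must be discontinued for a given participant if the investigator determines that continuing it would result in a significant safety risk". The next sentence adds: "This should only be done after discussion with and approval from the chief investigator/PI".
- **Section 6.5, second bullet.** "The following circumstances require study drug discontinuation". The first circumstance listed is "Emergence of severe adverse reactions such as severe nausea/vomiting, allergy, severe pruritus, anaphylaxis, and other life-threatening symptoms". This bullet does not repeat the approval sentence.
- **Section 7.2.** "Discontinuation of study drug may be considered if a participant experiences a severe adverse drug event of Grade 3 or higher". It continues: "Decision for discontinuation will be made by the PI and or the study participant".
- **Section 7.3.1.1.** If hypersensitivity or intolerance appears while ferric carboxymaltose is running, "the infusion must be stopped immediately, and the resuscitation protocol activated".

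Three definitions matter for reading these together. Table 4 (section 7.2.2) labels Grade 3 as severe and Grade 4 as life-threatening. The glossary treats study drug discontinuation as a permanent stop. Section 11.5 expects investigators to act at once for a participant's safety, even where that departs from the protocol.

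**The concern.** A site clinician facing a severe reaction finds two instructions. One says the drug has to be stopped for good; the other says stopping is a matter for consideration. They also route the decision differently, and nothing says which section governs.

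The first thing at stake is participant safety, because the protocol should give one answer for a severe reaction. The second is comparability across the 20 sites. Ferric carboxymaltose is a single infusion of 15 to 20 minutes, whereas oral ferrous sulphate runs to six weeks postpartum. Differences in how sites read the rule will therefore fall mainly on the oral arm. They would change how much iron control women receive, their recorded adherence (part of an objective in section 2.2) and who meets the 80% criterion for the Per Protocol set in section 9.3.

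**Working it through.** The core of this check is a comparison of text. The protocol states no figure on this point to reproduce.

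**1. Do the triggers overlap?** Section 6.5 speaks of severe adverse reactions and section 7.2 of severe adverse drug events of Grade 3 or higher. Table 4 is the protocol's own severity scale and gives severe as Grade 3. Taking severe in 6.5 to carry that meaning, the triggers coincide from Grade 3 upwards. One could try to separate them by reading 6.5 as covering only its named reactions and 7.2 as covering other Grade 3 events. The wording of 6.5 does not allow this, because its named reactions are examples of a general class. Life-threatening anaphylaxis, a named example in 6.5, is also Grade 4 under Table 4 and so falls within 7.2.

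**2. Do the obligations agree?** Section 6.5 requires discontinuation and section 7.2 permits it. For a severe reaction both cannot be the rule. No precedence statement or cross-reference resolves it.

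**3. Do the deciders agree?** In part.
- Section 6.5: the investigator judges the safety risk, with approval from the chief investigator/PI.
- Section 7.2: the PI, the participant, or both.
- The PI is common to both. The chief investigator appears only in 6.5, and a decision by the participant appears only in 7.2.

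**4. Does the approval sentence collide with the immediate infusion stop?** Not demonstrably. The approval sentence belongs to the first bullet of 6.5, and applying it to the list in the second bullet is an inference. Section 7.3.1.1 halts an infusion in progress, which is not the permanent stop of the glossary. What remains is an ambiguity: the infusion is a single dose, so halting it for anaphylaxis may in effect end study drug, and 6.5 names anaphylaxis without saying how its approval sentence relates to 7.3.1.1.

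**5. What can turn on the reading for one woman in the oral arm?** Inputs are two tablets a day to six weeks postpartum and 65 mg elemental iron per tablet (section 4.6.1, Table 2), and the 80% criterion (section 9.3).
- Full course: 2 × 42 = 84 tablets, or 84 × 65 = 5,460 mg. A start up to 48 hours after delivery removes at most 4 tablets, leaving 80.
- The 80% criterion: 0.80 × 84 = 67.2, so 68 tablets, reached after 68 / 2 = 34 days of full dosing. With 80 tablets: 0.80 × 80 = 64, reached after 32 days.
- Illustration: a woman stopped after 10 days has taken at most 2 × 10 = 20 tablets, or 20 × 65 = 1,300 mg. That is 20 / 84 = 24% of the course (20 / 80 = 25%).

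A woman permanently stopped at day 10 under 6.5 cannot enter the Per Protocol set. The same woman kept on drug under 7.2 could. Day 10 is chosen for illustration. How many women this would affect cannot be derived, because the documents give no rate of severe reactions.

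**The case against.** The strongest reply is that this is a wording inconsistency with little reach. The primary analysis follows the intention-to-treat principle (section 9.4). Section 6.5 keeps women who stop drug in follow-up to six months with all assessments. The 80% criterion affects only the Per Protocol set. The reasons for stopping are already recorded under both 6.5 and 7.2. The PI is named in both sections, and a participant's say in 7.2 fits her right to withdraw at any time. All of this stands, and it is why no effect on the primary result is claimed. It does not remove the conflict between a required and an optional stop.

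A reader might also infer more than the documents support:

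- **That every severe reaction needs prior approval before stopping, in conflict with the immediate stop in 7.3.1.1.** The approval sentence is not attached to the severe-reaction list, halting an infusion differs from permanent discontinuation, and 11.5 expects immediate safety action. Management of anaphylaxis is also referred to a separate administration protocol that is not at hand.
- **That leakage adds another stopping rule.** Section 7.3.1.2 tells staff to stop and find another vein, so permanent discontinuation is not in question.
- **That 7.2.7 is a rival rule because it lists "Study drug dosage adjusted/temporarily interrupted".** That section is a menu of possible actions for any adverse event. It is tied to no grade and also includes permanent discontinuation.
- **That discontinuation for adverse events is itself a trial outcome.** The aim is tolerability, and the listed outcome is the incidence of adverse drug events.

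**Conclusion.** The point holds in a limited form and should be corrected. For a drug reaction of Grade 3 or higher, sections 6.5 and 7.2 give incompatible instructions on whether study drug must be discontinued, and they assign the decision to only partly matching roles. This rests on reading severe in 6.5 by the protocol's own grading in Table 4. The relation of the 6.5 approval sentence to 7.3.1.1 is an ambiguity that needs a clarifying sentence; it is not a third contradictory rule.

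The consequence is possible variation between sites in handling the same reaction, mainly in the oral arm. It bears on safety, iron received, adherence and per-protocol membership. For one woman it can decide whether she meets the 80% criterion. Its size across the trial, and any effect on the intention-to-treat result, is not quantified.

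**What to change.** Reconcile sections 6.5 and 7.2 into one stopping rule, kept in one place, to which the other section refers. For each grade or event, use a single term, required or considered, and state one decision-maker. Add a cross-reference saying how the approval sentence in 6.5 relates to the immediate infusion stop in 7.3.1.1. Which clinical rule is adopted, and how approval is handled, is for the investigators and the DSMB.

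The cost is a wording amendment, the ethics approval that section 11.5 requires for it, and a retraining note to sites. It needs no extra visits, staff or participants. No new data item is needed, since the reasons for stopping are already collected.

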6.6 Treatment exposure and compliance

- All medication (other than study drug) and significant non-drug therapies administered after the patient starts treatment with study drug will be documented under concomitant medications/significant non-drug therapies in the e-CRF after start of study drug.
- Records of study medications used, and exact dosage administration and compliance will be kept during the study.
- Drug accountability will be noted by the clinical monitor during site visits and at the completion of the study.

7 ADVERSE EVENTS AND REPORTING REQUIREMENTS

7.1 Adverse Events

- An adverse event (AE) is the appearance or worsening of any undesirable sign, symptom, or medical condition occurring after starting the study drug even if the event is not considered to be related to study drug. Study drugs include the investigational drug/ control drug under evaluation that is given during the treatment phase of the study.
- Medical conditions/diseases present before starting study drug are only considered adverse events if they worsen after starting study drug.
- Abnormal laboratory values or test results constitute adverse events only if they induce clinical signs or symptoms, or are considered clinically significant, or require therapy. E.g., hypophosphatemia requiring treatment.
- Clinical signs and symptoms will be assessed at baseline, before dosing and at all follow-up visits, and recorded in the e-CRF. Any symptom that worsens or starts after baseline will be recorded as a new adverse event on the e-CRF.
- The occurrence of adverse events, such as fever, weakness, chills/rigors, headache, myalgia, dizziness, epigastric pain, abdominal pain, anorexia, nausea, vomiting, diarrhea, palpitations, insomnia, pruritus, coughing, tinnitus, abnormal gait, tremor, clonus, or dyskinesia, will be sought by the investigator (or designee) at each study visit and recorded in the e-CRF.
- Adverse events also may be detected when they are volunteered by the patient during or between visits or through physical examination, laboratory test, or other assessments.

7.2 Reporting Adverse Events (AEs)

- All adverse events that occur from the point of enrollment and throughout study duration will be collected non-systematically from each participant. Participants will be routinely asked at every study visit "do you have any symptoms now or noticed any since your last visit?"
- If a participant reports an AE at enrollment but before the administration of study intervention, the AE will be reported as not related to study drug. All other adverse events reported after enrollment into the study and until the end of study will be defined and graded for severity using the National Cancer Institute Common Terminology Criteria for Adverse Events version 5.0
- Study site coordinators/clinician will document on the appropriate study e-CRF, and clinical case notes all AEs reported by or observed in enrolled study participants regardless of severity and presumed relationship to study product.
- The study clinician must provide on the AE e-form information on symptoms, time of onset, severity, frequency, product-relatedness, actions taken and participant outcome.
- The causality of AE to trial drugs will be determined by the principal investigator and documented along with the interventions given, and the outcome.
- The PI may request additional information from the site if it is needed to further evaluate the AE.

- Site coordinators will report serious adverse events (SAEs; see section 7.2.5) to the principal Investigator and the local Ethics committee as soon as possible and in accordance with the local ethics committee requirements.
- Discontinuation of study drug may be considered if a participant experiences a severe adverse drug event of Grade 3 or higher. Decision for discontinuation will be made by the PI and or the study participant. Study personnel will document the circumstances and data leading to discontinuation.

All adverse events must be recorded on the e-CRF with the following information:

- 1. Event (nomenclature/description) (See section 7.2.1)
- 2. The severity grade (mild, moderate, severe, life threatening or death) (see section 7.2.2)
- 3. Its relationship to the study drug(s) (see section 7.2.3)
- 4. Its duration (start and end dates or if continuing at final physical exam)
- 5. Whether it constitutes a serious adverse event (SAE)
- 6. Action taken (Treatment)
- 7. Outcome

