1.1 Background

Anemia in pregnancy is a major public health burden with a high incidence in low- and middle-income countries (LMICs) such as Nigeria (1). It is most commonly caused by iron deficiency, which accounts for 50–75% (2). Postnatal anemia may result from untreated antenatal anemia or as a result of blood loss that occurs during birth. (3), and its prevalence in LMICs has been estimated to range from 50 to 80% (4). A study in Eastern Nigeria found anemia at 48 hours and six weeks postpartum to be 73% and 48% respectively, in a cohort of 202 women followed from late pregnancy until six weeks postpartum (5).

Anemia and iron deficiency anemia in pregnancy lead to increased morbidity and mortality for the mother and affects the neonates adversely (6). Specifically, postnatal anemia increases the risk of infection, leads to poor wound healing, and causes fatigue and depression in the mother (7). It also adversely affects breastfeeding, due to insufficient milk production, can reduce bonding between women and their newborn as a result of weakness and fatigue (3, 4, 8).

Oral iron is used routinely for the treatment of mild to moderate anemia in the postnatal period, while blood transfusion is offered for severe anemia or symptomatic women with moderate anemia (3). Oral iron, though inexpensive, causes significant gastrointestinal adverse effects such as vomiting, constipation, diarrhea, and abdominal pain (9), limiting adherence to this vital intervention which may pose a challenge in achieving optimum correction of anemia by the end of the postnatal period. Adherence to oral iron is reportedly low, with only 16% of women fully compliant with their treatment in a study among pregnant women in Cameroon, one of Nigeria's neighboring countries (10).

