7.3.2.2 Gastro-intestinal disorders

Abdominal discomfort and anorexia, abdominal pain, nausea, and vomiting (these are usually dose related), constipation, diarrhea, and dark stools. Contact irritation can occur with ferrous sulphate tablets resulting in erosion or ulceration, particularly if they become lodged in the upper gastrointestinal tract.

Caution:

- Ask patients to keep medication out of the sight and reach of children, as overdose may be fatal.
- Ask about previous allergy to iron formulations.
- Administer oral FS with caution in patients with existing gastrointestinal disease like difficulty in swallowing and inflammatory bowel diseases.
- Due to the risk of mouth ulcerations and tooth discoloration, tablets should not be sucked, chewed, or kept in the mouth but swallowed whole with water.
- Advise to take FS 1 hour before meals or 2 hours after meals with a full glass of water

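### Sections 7.1 and 7.2 prescribe different ways of collecting adverse events, and the symptoms to be sought in 7.1 leave out constipation and dark stools

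*Protocol*

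**What the plan says.** Section 7.1 describes solicited collection. It names adverse events "such as fever, weakness, chills/rigors, headache, myalgia, dizziness, epigastric pain, abdominal pain, anorexia, nausea, vomiting, diarrhea" and continues "palpitations, insomnia, pruritus, coughing, tinnitus, abnormal gait, tremor, clonus, or dyskinesia, will be sought by the investigator (or designee) at each study visit". It then adds further routes, the last of them open-ended: "Adverse events also may be detected when they are volunteered by the patient during or between visits or through physical examination, laboratory test, or other".

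Section 7.2 describes something else: "All adverse events that occur from the point of enrollment and throughout study duration will be collected non-systematically from each participant". The prompt it gives is a single open question put at every visit: "do you have any symptoms now or noticed any since your last visit". The same section has site staff document every event reported or observed, whatever its severity or presumed cause.

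On what to expect from oral iron, 7.3.2.2 lists: "Abdominal discomfort and anorexia, abdominal pain, nausea, and vomiting (these are usually dose related), constipation, diarrhea, and dark stools". The background in 1.1 says that oral iron "causes significant gastrointestinal adverse effects such as vomiting, constipation, diarrhea, and abdominal pain" and that this limits adherence.

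Tolerability and safety are part of aim (a) in 2.1. The incidence of adverse drug events is secondary outcome (q) in 3.1.2. Section 7.4 plans to report absolute risk, incidence and severity grade by arm.

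**The concern.** Prompting for named symptoms and asking one general question are different ways of finding adverse events and can be expected to yield different counts. In 7.2 the word all leaves no subset of events for the active seeking in 7.1, and the word non-systematically works against reading the two sections as a planned combination. Staff at 20 sites could follow either section and believe they were complying.

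The named symptoms also fit the control drug unevenly. A nurse working through the 7.1 examples would ask about nausea, vomiting, diarrhea and abdominal pain, but not about constipation or dark stools. Those two would then depend on the general question or on the woman raising them. Constipation is one of the effects that 1.1 ties to poor adherence, so it is central to the tolerability comparison. This is a matter of data capture: no later analysis can recover a symptom that was never elicited.

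**Working it through.** The documents give no adverse event rates, so there is no figure of the plan's to reproduce. The check is a comparison of texts, followed by the algebra of incomplete capture.

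**Step 1: method.**
- 7.1: named symptoms are sought by the investigator or a designee at each visit. This is solicited collection.
- 7.2: all events are collected non-systematically, by one open question. This is unsolicited collection.
- Neither section says that the open question comes first and the named symptoms follow, or that one section governs.

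**Step 2: terms.** Section 7.1 names 21: fever, weakness, chills/rigors, headache, myalgia, dizziness, epigastric pain, abdominal pain, anorexia, nausea, vomiting, diarrhea (12), then palpitations, insomnia, pruritus, coughing, tinnitus, abnormal gait, tremor, clonus, dyskinesia (9). Against the symptoms that open 7.3.2.2:

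| Ferrous sulphate effect in 7.3.2.2 | Also in 1.1 | Among the 7.1 terms |
|---|---|---|
| Abdominal discomfort | no | only through abdominal or epigastric pain |
| Anorexia | no | yes |
| Abdominal pain | yes | yes |
| Nausea | no | yes |
| Vomiting | yes | yes |
| Constipation | yes | **no** |
| Diarrhea | yes | yes |
| Dark stools | no | **no** |

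Five of the eight match, one is covered indirectly and two are absent. Section 7.4, in its own examples of anticipated reactions, names neither of the two.

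**Step 3: effect on the comparison.** Let p_o and p_v be the true risks of a symptom on oral and IV iron, and s the fraction of cases captured, equal in both arms and with no false positives.
- Observed risks: s × p_o and s × p_v.
- Observed risk ratio: (s × p_o) / (s × p_v) = p_o / p_v, unchanged.
- Observed risk difference: s × (p_o − p_v), shrunk by the factor s.

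Illustration only; every input is assumed and none comes from the protocol. Take p_o = 15% and p_v = 5%, a true difference of 10 points and a ratio of 3.
- s = 0.3: 4.5% against 1.5%, difference 3 points, ratio 3.
- s = 0.7: 10.5% against 3.5%, difference 7 points, ratio 3.

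Other true risks change the starting difference but not the factor. If s is high for prompted symptoms and lower for unprompted ones, absolute incidence is not comparable between terms within the same arm. If capture differed between arms, the ratio would also move, by the factor s_o / s_v. The documents give no basis for a value of either.

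**The case against.** Much of the case on the other side stands.

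- The 7.1 terms are introduced as examples, so leaving one out does not exclude it.
- Section 7.1 has clinical signs and symptoms assessed at baseline and at all follow-up visits. Sections 4.10.3 and 4.10.5 have staff evaluate any symptom or sign at each visit, and Table 3 schedules both symptoms and adverse events at every visit. Women in both arms are therefore asked routinely, although not term by term.
- All sites enter data on the same REDCap forms. The adverse event e-form (Appendix ix) and the abridged CTCAE list (Appendix xix) are not shown and may name constipation.
- Section 4.5 says that the nurse collecting the adverse event form is blinded, which limits assessor bias. Women know their treatment under either method, so a checklist does not remove expectation effects.
- Randomization is stratified by site (4.4), which largely protects the between-arm comparison from differences in method between sites.

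Two stronger readings are tempting. A reader might infer that constipation and dark stools will be missed; the provisions above show that they can be recorded, so only under-recording is a supported risk. A reader might also infer a gap for hypotension and infusion-site effects, since neither is a named symptom in 7.1. The documents do not support that: blood pressure is measured at each visit (4.8), vital signs are part of safety assessment (7.3), infusions are monitored (7.3.1.1) and leakage with skin discoloration is addressed in 7.3.1.2.

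What the objection does not remove is the conflict between 7.1 and 7.2, or the uneven prompting if the 7.1 examples are used as written. Stratification and blinding protect neither absolute incidence nor comparability between terms.

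**Conclusion.** The point holds as a contradiction in the protocol text, together with a mismatch between the symptoms named in 7.1 and the control-drug effects named in 7.3.2.2. The consequence is a risk of under-recording constipation and dark stools, and of absolute incidence that is uneven by term and by site, for outcome (q) and the tolerability aim. The primary outcome is not affected.

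The size is unknown. With equal capture in both arms and no false positives, the relative comparison is preserved and the absolute one is diluted by the capture fraction. The conclusion about term-by-term unevenness assumes that staff use the 7.1 examples as their prompts and that the forms not shown do not already correct for this. If Appendix ix already carries a fixed list with both terms, what remains is a wording conflict between the two sections.

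**What to change.** Delete the word non-systematically from 7.2 and state one method, in the same terms in 7.1 and 7.2, for all sites and both arms:

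1. Ask the open question first.
2. Then go through a fixed symptom checklist on the adverse event e-form. Keep the existing 7.1 terms, including the neurological ones, whose removal would resolve no contradiction and would narrow safety capture. Add constipation and dark stools.
3. Flag each event as volunteered or solicited, so that the two can be reported separately.
4. Complete the checklist after the other patient-reported forms at that visit, because some items, such as dark stools, may hint at allocation to the nurse described as blinded in 4.5. Sections 4.10.3 and 4.10.5 already list the forms in this order; make it a requirement.

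The cost is a wording amendment and an edit to one e-form, with no added visits. The downsides are slightly longer visits, more mild events on record and a small remaining risk of unblinding that nurse.
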